### **5.2.2 Timing of Dose Administration**

Trial pembrolizumab treatment should be administered on Day 1 of each 3 week pembrolizumab cycle after all procedures or assessments have been completed as detailed on the Trial Flow Chart (Section 6.0), within the specified window. Trial treatment may be administered up to 3 days before or after the scheduled Day 1 of each cycle due to administrative or other practical reasons.

Pembrolizumab 200 mg target infusion time is to be 30 minutes. However, given the variability of infusion pumps, a window of -5 minutes and +10 minutes is permitted (*i.e.*, infusion time is 30 minutes: -5 min/+10 min, which is 25 to 40 minutes).

The Pharmacy Manual contains specific instructions for the preparation of the pembrolizumab infusion fluid and administration of infusion solution.

*Terminology notes:*

To keep with most of the pembrolizumab development, one “cycle” is designated as a 3 week span of time with one dose of pembrolizumab on the first day. To avoid confusion, for this document, the term “cycle” will be avoided for the IL-2 treatment courses, or for the time in between CT scans.

One “block” for protocol purposes is a group of three (or four) pembrolizumab cycles. The pembrolizumab cycles are numbered a #1, #2, and #3. A fourth cycle will be designated as #4e”, where “e” means extra, for an extra pembrolizumab-only 3-week cycle added to accommodate *any* scheduling issues.

There are eight hospital admissions for IL-2 treatment, which are in the second and third weeks on the first and second cycles of the second and third blocks. These will be designated by the approximate week within the block, using B2 for the second block and B3 for the third block, and thus, for B2: B2W2, B2W3, B2W5, B2W6, and correspondingly for B3W2, B3W3, B3W5 & B3W6.

Since the “week” designation can be affected by intervals that are permissible (such as 6 days, that would technically be during the same (*conventional definition*) calendar week, the protocol document will avoid designating the IL2 doses as being scheduled within a particular “week”, but instead will use the abbreviations defined above. (B2W2, etc.) where possible.

This is the whole schedule:

*Start of block B1:*

Cycle 1 pembrolizumab dose 1. Interval to next dose  $21 \pm 3$  days.

Cycle 2 pembrolizumab dose 2. Interval to next dose  $21 \pm 3$  days.

Cycle 3 pembrolizumab dose 3. Interval to next dose  $21 \pm 3$  days.

End of block 1: 21 days after third pembrolizumab dose, or first pembrolizumab dose of next cycle, or 87 days after start. (This accommodates possible insertion of a “#4e” extra cycle of pembrolizumab, if needed).

*Start of block B2:*

Cycle 1 pembrolizumab dose 1. Interval to next dose  $21 \pm 3$  days.

IL2 admission designated as “B2W2”: Usually 7 days, but target 2-9 days after block 2 cycle 1 pembrolizumab.

IL2 admission designated as “B2W3”: Usually 7 days, but target 6-9 days after B2W2.

Cycle 2 pembrolizumab dose 2. At least 3 days but usually 7 days, or up to 10 days after B2W3. Interval to next pembrolizumab dose  $21 \pm 3$  days.

IL2 admission designated as “B2W5”: Usually 7 days, but target 2-9 days after block 2 cycle 2 pembrolizumab.

IL2 admission designated as “B2W6”: Usually 7 days, but target 6-9 days after B2W5.

Cycle 3 pembrolizumab dose 3. Interval to next dose  $21 \pm 3$  days.

End of block B2: 21 days after third pembrolizumab dose, or first pembrolizumab dose of next cycle, or 87 days after start of the first pembrolizumab dose of the block (If “#4e” used.)

*Start of block B3:*

Cycle 1 pembrolizumab dose 1. Interval to next dose  $21 \pm 3$  days.

IL2 admission designated as “B3W2”: Usually 7 days, but target 2-9 days after block 2 cycle 1 pembrolizumab.

IL2 admission designated as “B3W3”: Usually 7 days, but target 6-9 days after B3W2.

Cycle 2 pembrolizumab dose 2. At least 3 days but usually 7 days, or up to 10 days after B2W3. Interval to next pembrolizumab dose  $21 \pm 3$  days.

IL2 admission designated as “B3W5”: Usually 7 days, but target 2-9 days after block 2 cycle 2 pembrolizumab.

IL2 admission designated as “B3W6”: Usually 7 days, but target 6-9 days after B3W5.

Cycle 3 pembrolizumab dose 3. Interval to next dose  $21 \pm 3$  days.

End of cycle 3: 21 days after third pembrolizumab dose, or first pembrolizumab dose of next cycle, or 87 days after start of the first pembrolizumab dose of the block. (If cycle #4e is used.)

*Start of block B4:*

Cycle 1 pembrolizumab dose 1. Interval to next dose  $21 \pm 3$  days.

Cycle 2 pembrolizumab dose 2. Interval to next dose  $21 \pm 3$  days.

Cycle 3 pembrolizumab dose 3. Interval to next dose  $21 \pm 3$  days.

End of block 4: 21 days after third pembrolizumab dose. A cycle #4e may be used if a scan delay is anticipated. The end of block 4 is the end of the treatment phase of the study.

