## **2.1 TRIAL DESIGN**

### **2.2 Trial Design**

Overall schedule plan: The treatment is organized into blocks of 9 weeks, with pembrolizumab treatment planned for weeks 1, 4 and 7. On the second and third blocks, interleukin-2 is added, for 5 doses at a time, one dose every 8 hours, on a weekly schedule on the two weeks after the week 1 and the week 4 pembrolizumab doses. This works out to a plan of 20 doses per 9 week block. The fourth block is again pembrolizumab monotherapy, as was the first. If delays occur prior to the 2nd or 3rd block, up to one additional 3 week (one dose) pembrolizumab dose may be added, to keep the overall pattern, within the second and third blocks. If a complete response is identified (including after block 1), then pembrolizumab can be continued as specified to the end of block 4, or stopped sooner after at least 2 interval scans showing complete response, at the discretion of the treating physician or the study PI. The protocol specified treatment finishes after the end of the 4th block. This will typically be 36 weeks after start, but extra 3-week cycles of pembrolizumab are allowed, if needed to maintain the overall schedule, so duration of treatment may turn out to be a month or two longer.

There is no dose escalation portion: The dose and schedule of IL-2 is fixed, 600,000 IU/kg/dose, with a cap of 66 mIU/dose. Doses may be omitted for safety. The dose of pembrolizumab is fixed, flat dose 200 mg/dose.

Safety monitoring: Sequential boundaries will be used to monitor dose-limiting toxicity rate. There is a detailed plan in section 8.5

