## **2.4 Trial Diagrams**

### **2.4.1 Treatment intervals**

*Key features:* In the absence of schedule adjustments, all treatment starts (pembrolizumab or IL-2 admission) could be the same day of the week.

[figure not shown]
At least 5 days between the end of IL-2 admission and next pembrolizumab infusion gives time for resolution of IL-2 side effects before the irAE assessment before the next pembrolizumab dose.

FIGURE 2: DOSE DAYS INTERVAL DIAGRAM

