## 5.2 Trial Treatments

The treatment to be used in this trial is outlined below in Table 2

Table 2 Trial Treatment

| Drug          | Dose/Potency                              | Dose Frequency | Route of Administration                | Regimen/Treatment Period                                                                                                                                                     | Use          |
|---------------|-------------------------------------------|----------------|----------------------------------------|------------------------------------------------------------------------------------------------------------------------------------------------------------------------------|--------------|
| Pembrolizumab | 200 mg                                    | Q3W            | IV infusion outpatient                 | Every 21d ± 3d                                                                                                                                                               | Experimental |
| Interleukin-2 | 15 minute infusion of 600,000 IU/kg/dose* | q8h x5         | IV infusion over 15 minutes, inpatient | Two courses set after corresponding pembrolizumab that defines day 1 of the cycle with intervals of:
P → W1: 2-9 days, usually 7 days
W1 → W2: 6-9 days usually 7 days | Standard     |

\*actual body weight; capped at 66 million IU/dose for subjects > 110 kg.  
P = date of pembrolizumab dose  
W1 = date of first IL-2 dose of the course  
W2 = date of first IL-2 dose of the next course

Trial treatment should begin as close as practical to the date on which eligibility is established and treatment level is allocated (for those patients on the part of the trial where the pembrolizumab dose is still not fixed).

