**Note: Permanently discontinue for any severe or Grade 3 drug-related AE that recurs or any life-threatening event.**

 For patients with liver metastasis who begin treatment with Grade 2 AST or ALT, if AST or ALT increases by greater than or equal to 50% relative to baseline and lasts for at least 1 week then patients should be discontinued.

 Patients with intolerable or persistent Grade 2 drug-related AE may hold study medication at physician discretion. Permanently discontinue study drug for persistent Grade 2 adverse reactions for which treatment with study drug has been held, that do not recover to Grade 0-1 within 12 weeks of the last dose.

Dosing interruptions are permitted in the case of medical / surgical events or logistical reasons not related to study therapy (e.g., elective surgery, unrelated medical events, patient vacation, and/or holidays). Subjects should be placed back on study therapy within 3 weeks

of the scheduled interruption, unless otherwise discussed with the Sponsor. The reason for interruption should be documented in the patient's study record.

*Note: These evaluations should be done in relation to each pembrolizumab dose. Adverse events that occur or are noted in between scheduled pembrolizumab infusions, but are within 2 weeks after IL-2 administration and appear to meet Table 3 criteria, and have resolved at the point of the next pembrolizumab dose, and are attributed to the IL-2 treatment's acute side effects do not count as events that are required to be managed as indicated in Table 3. For example, grade 3 creatinine elevation that resolved after the IL-2 was finished but before the next pembrolizumab infusion would not count as an AE that requires interruption of the pembrolizumab treatment schedule.*

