*Note: Every event, such as isolated hypotension or oliguria or elevation of creatinine should be critically evaluated for attribution to IL-2 or to pembrolizumab. Those occurring after IL-2 treatment should be expected to have resolved before the next pembrolizumab infusion, which is at least 6 days later.*

| NCI CTCAE Grade                                                                                                                                                                                | Treatment                                                                                                                                                                                                                                         | Premedication at subsequent dosing                                                                                                                                                                                                                      |
|------------------------------------------------------------------------------------------------------------------------------------------------------------------------------------------------|---------------------------------------------------------------------------------------------------------------------------------------------------------------------------------------------------------------------------------------------------|---------------------------------------------------------------------------------------------------------------------------------------------------------------------------------------------------------------------------------------------------------|
| Grade 1
Mild reaction; infusion interruption not indicated; intervention not indicated                                                                                                      | Increase monitoring of vital signs as medically indicated until the subject is deemed medically stable in the opinion of the investigator.                                                                                                        | None                                                                                                                                                                                                                                                    |

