### **7.1.2 Clinical Procedures/Assessments**

#### **7.1.2.1 Adverse Event (AE) Monitoring**

The investigator or qualified designee will assess each subject to evaluate for potential new or worsening AEs as specified in the Trial Flow Chart and more frequently if clinically indicated. Adverse experiences will be graded and recorded throughout the study and during the follow-up period according to NCI CTCAE Version 4.0 (see Section 11.2). Toxicities will be characterized in terms regarding seriousness, causality, toxicity grading, and action taken with regard to trial treatment.

For subjects receiving treatment with pembrolizumab all AEs of unknown etiology associated with pembrolizumab exposure should be evaluated to determine if it is possibly an event of clinical interest (ECI) of a potentially immunologic etiology (termed immune-related adverse events, or irAEs); see the separate ECI guidance document regarding the identification, evaluation and management of potential irAEs.

Note: Events that are consistent with the expected adverse events of IL-2 therapy, as annotated on the Proleukin™ prescribing information, and which resolve along the expected time course (generally within a few days) are to be distinguished from pembrolizumab irAEs.

Please refer to section 7.2 for detailed information regarding the assessment and recording of AEs.

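### The dosing schedule allows pembrolizumab sooner after an IL-2 admission than the 5-day and 6-day minimums stated elsewhere, and sets no minimum before the cycle 3 dose

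*Combined protocol and SAP*

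**What the plan says.** Three places give a minimum interval between IL-2 and the next pembrolizumab dose.

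- Section 2.4.1, beside the trial diagrams: "At least 5 days between the end of IL-2 admission and next pembrolizumab infusion gives time for resolution of IL-2 side effects". The sentence goes on to place that resolution ahead of the irAE assessment before the next dose.
- Section 5.2.2 (Timing of Dose Administration), for cycle 2 of block B2: "At least 3 days but usually 7 days, or up to 10 days after B2W3". Block B3 repeats the line with the same B2W3 label. The lines for cycle 3, after B2W6 and B3W6, give no minimum.
- Section 5.7.1, note introducing Table 4, on events after IL-2: they "should be expected to have resolved before the next pembrolizumab infusion, which is at least 6 days later".

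Section 5.2.2 also says "Trial treatment may be administered up to 3 days before or after the scheduled Day 1 of each cycle". It does not say whether the 3 days run from the first IL-2 dose or from discharge. Table 2 in Section 5.2 dates IL-2 courses by first dose ("W2 = date of first IL-2 dose of the next course").

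Block B3 carries two further block 2 labels: B3W2 and B3W5 are timed from block 2 pembrolizumab doses.

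**The concern.** Section 5.2.2 is the schedule that a site will follow, and its minimum is lower than the one whose safety purpose is stated in Section 2.4.1. A site can comply with it and still carry out the pre-dose immune assessment while acute IL-2 effects are present, which makes attribution between the two drugs harder.

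Two rules depend on that moment. The note after Table 3 (Section 5.2.1.2) exempts IL-2 events from Table 3 management only if they are attributed to IL-2 "and have resolved at the point of the next pembrolizumab dose". Section 8.5 excludes typical IL-2 events from the DLT count only if they have resolved when the next pembrolizumab dose is due, and that count feeds the accrual-suspension boundary. A shorter gap leaves less time for an event to qualify for either exemption. Section 4.4.4.1 describes the trial as the initial human experience with the two drugs together on this schedule, so clean attribution matters.

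**Working it through.** **Inputs.** Pembrolizumab is day 0. From Section 5.2.2 and Table 2:

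- first IL-2 course on day a, with a = 2 to 9 (usually 7);
- second course b days later, with b = 6 to 9 (usually 7);
- next pembrolizumab on day P = 18 to 24 (21 ± 3).

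This gives 8 × 4 = 32 IL-2 date combinations and 32 × 7 = 224 whole-day schedules. Section 4.4.2 puts each admission at 3 days. I assume discharge falls L = 2 days after the first dose of the course and vary L below.

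**Formulas.** Gap from first dose = P − (a + b). Gap from discharge = P − (a + b + L).

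**The plan's 5 days.** On usual dates a + b = 14 and discharge is day 16, so 21 − 16 = 5. The stated minimum is reproduced, but only as the value for the usual schedule dosed on day 21.

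**The 6 days in Section 5.7.1.** IL-2 is given "for 5 doses at a time, one dose every 8 hours", so the first-to-last-dose span is 4 × 8 = 32 hours, or 1.33 days. Day 21 is then 7 − 1.33 = 5.67 days after the last dose. That is 6 calendar days if the last dose falls on the day after the first; a first dose at 16:00 or later pushes it to the day after that.

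**Usual IL-2 dates, early pembrolizumab.** Days 18, 19 and 20 fall 18 − 16 = 2, 19 − 16 = 3 and 20 − 16 = 4 days after discharge. Before cycle 3 all three days are allowed. Before cycle 2 all three are allowed if the 3-day rule runs from the first dose (gaps 4, 5 and 6), and days 19 and 20 if it runs from discharge.

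**All permitted schedules, L = 2.**

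| Transition and rule | Permitted | Under 5 days after discharge | Shortest gap |
|---|---|---|---|
| To cycle 2, 3 to 10 days from first dose | 162 | 64 | 1 day |
| To cycle 2, 3 to 10 days from discharge | 170 | 40 | 3 days |
| To cycle 3, no minimum | 224 | 74 | −2 days |

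Example of the 1-day gap: a = 9, b = 9, P = 21. The first-dose gap is 21 − 18 = 3, discharge is day 20, and 21 − 20 = 1. The −2 is the same IL-2 dates with P = 18.

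**Sensitivity to the stay.** With the rule from first dose, 42, 64 or 89 of 162 schedules are under 5 days for discharge on day +1, +2 or +3.

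**Effect of a 5-day minimum from discharge, L = 2.** Schedules left: 162 − 64 = 98 or 170 − 40 = 130 before cycle 2, and 224 − 74 = 150 before cycle 3. Meeting it by day 24 needs a + b + 2 + 5 ≤ 24, so a + b ≤ 17, which excludes only 9 + 9 (1 of 32). With L = 3 it needs a + b ≤ 16, which excludes 8 + 9, 9 + 8 and 9 + 9 (3 of 32). Keeping day 21 itself needs a + b ≤ 14; 10 of the 32 combinations exceed that.

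**The case against.** The best defence is that Section 2.4.1 is not a rule. It introduces its key features as holding when no schedule adjustment is made, the 5-day sentence reads as a rationale, and 5 days is just what the usual dates give. The accompanying figures are not available here and may state an anchor. On that view Section 5.2.2 is the only operative text. This is a fair reading, but the sentence says at least and gives a safety reason, Section 5.7.1 also says at least, and day 18 is permitted even when IL-2 is on its usual dates.

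The second defence is that the safety purpose is met elsewhere, and this largely stands. Section 5.2.1.2 requires evaluation at each pembrolizumab dose and a grade that the investigator judges safe. Section 7.1.2.1 separates the drugs by time course: IL-2 events "which resolve along the expected time course (generally within a few days) are to be distinguished from pembrolizumab irAEs". A reader might infer that the schedule licenses dosing through IL-2 toxicity. It does not, because those checks apply whatever the interval.

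A reader might also take 64 of 162 as a share of patients. It counts permitted date combinations, with edge dates weighted equally with usual ones; the documents give no actual frequencies. Nor does the negative gap before cycle 3 mean that overlap is planned. Table 2 makes pembrolizumab an outpatient infusion, so the figure shows only that a minimum is missing.

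**Conclusion.** The inconsistency is real and holds under either anchor. Section 5.2.2 allows less than the 5 days of Section 2.4.1 and the 6 days of Section 5.7.1 before cycle 2, and sets no minimum before cycle 3. The exact counts rest on the assumed discharge day; the conflict does not, since 3 days from discharge is below 5 and 3 days from the first dose is shorter still.

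The safeguard is weakened, not removed. It would be too strong to say that the trial's main inference is compromised, because the Simon design and the sample size do not depend on this interval. It would be too weak to say that nothing in the analysis depends on it, because Table 3 management and the Section 8.5 DLT count both turn on resolution by the next pembrolizumab dose. The wording should be corrected.

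**What to change.** In Section 5.2.2, at all four transitions (B2W3 and B3W3 to cycle 2; B2W6 and B3W6 to cycle 3), require pembrolizumab at least 5 days after the end of the IL-2 admission, usually 7 days after the first IL-2 dose of that course. State that this overrides the early side of the ±3-day window. Counting from the end of the admission keeps the protection when a stay runs long; a 7-day minimum from the first dose would not, since with discharge on day +3 the gap would be 7 − 3 = 4 days.

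Keep the 10-day limit before cycle 2 and state its anchor. Add no upper limit before cycle 3, where none exists and no safety reason calls for one. Align the Section 5.7.1 note with the same minimum. In block B3, change B2W3 to B3W3, and block 2 to block 3 in the B3W2 and B3W5 lines.

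The cost is wording plus some flexibility. On usual IL-2 dates days 18 to 20 are lost and day 21 stays. With discharge on day +2, the 10 later IL-2 combinations can no longer use day 21; 9 of them can still be dosed by day 24, and 9 + 9 cannot. With discharge on day +3, 3 of 32 combinations cannot meet the minimum by day 24.

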### **5.2.3 No Trial Blinding**

This is an open-label trial; therefore, the Sponsor, investigator, staff, and subject will know the treatment administered.

#### 5.2.4 IL-2 treatment checklist, before each IL-2 dose.

Note: This list does not supersede the treating physician judgment on whether to withhold a dose or not.

Lab results – refer to most recent results, generally fewer than 28 hours old.

- a. No current use of steroids or other anti-immune treatments prescribed for management of autoimmune problems. (Use of glucocorticoids for patients who are hypoadrenal is allowed).
- b. No Grade 2 or worse ongoing pembrolizumab-attributed events (Table 6b).
- c. Patient willingness to take another IL-2 dose – query nausea, motivation.
- d. Not requiring oxygen supplement 2L/min or less for oxygen saturation of 90% or more.
- e. Most recent creatinine level should be:
  - a. under 150% of baseline value to start a course
  - b. under 250% of baseline at most recent evaluation for later doses in the same course. (see note on physician judgment)
- f. Systolic blood pressure above target level:
  - a. i. Target = 80 mmHg if baseline was <100
  - b. ii. Target = 85 mmHg if baseline was 100-120
  - c. iii. Target = 90 mmHg if baseline was 120+ mmHg systolic
- g. If atrial fibrillation is present—treating physician evaluation on per-case basis.
- h. Heart rate not documented as continuously 120 for more than 1 hour (during prior 8 hours).
- i. Dopamine off, or less than or equal to 2 mcg/kg/min.
- j. Urine output > 150 ml over last 8 hours.
- k. Two or fewer 500 ml NS bolus had been required in last 8 hours for treating blood pressure or urine output.
- l. Electrolytes and liver function tests should be reviewed by treating physician.

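### Item d of the pre-dose IL-2 checklist (section 5.2.4) is miswritten: taken literally it holds a dose for oxygen need up to 2 L/min but not above, and no other section states the limit

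*Combined protocol and SAP*

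**What the plan says.** Section 5.2.4 is headed "IL-2 treatment checklist, before each IL-2 dose". Item d, its only line on oxygen, is "Not requiring oxygen supplement 2L/min or less for oxygen saturation of 90% or more".

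Neighbouring items show how the list works. Item j is "Urine output > 150 ml over last 8 hours" and item i is "Dopamine off, or less than or equal to 2 mcg/kg/min". Item k accepts at most two 500 ml saline boluses in the preceding 8 hours. Each states what must be true for the dose to go ahead. Items a and b take a different form and require that something be absent: current immunosuppression for autoimmune problems (a), and ongoing Grade 2 or worse events attributed to pembrolizumab (b).

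The list opens with a caveat: "This list does not supersede the treating physician judgment on whether to withhold a dose or not".

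**The concern.** A pre-dose oxygen criterion should become harder to pass as oxygen need rises. Item d does the reverse once need is above zero: its words exclude the smaller need and are silent on the larger one. The line is an operative dosing threshold, so this is more than a typing slip in background text.

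At stake is the clarity of one safety rule in a regimen that section 4.4.4.1 describes as the first human experience of the two drugs together on this schedule. Section 4.4.2 names dyspnea among the events that end high-dose IL-2 courses, so respiratory status is relevant to the decision to give the next dose. A reader who looks for the intended limit elsewhere will not find it.

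**Working it through.** The plan states no figure to reproduce here, so the check is a logical one.

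**Step 1: direction of the list.** Items i, j and k are all conditions for going ahead. Failing one points to holding the dose. Item d sits in the same list and is read the same way.

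**Step 2: apply item d literally.** The item is met when the patient is not in the state of requiring 2 L/min or less to keep saturation at 90% or above. Two other readings are possible. The ceiling reading assumes that a connecting word was lost, giving none, or up to 2 L/min, as in item i. The strict reading takes the line to mean that not even 2 L/min may be needed.

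| Oxygen needed to keep saturation at 90% or above | Literal text | Ceiling reading | Strict reading |
|---|---|---|---|
| 0 L/min | clear | clear | clear |
| above 0 to 2 L/min | hold | clear | hold |
| above 2 L/min | clear (not caught) | hold | hold |

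The literal text departs from both sensible readings in the bottom row. The two sensible readings agree there and differ only in the middle row.

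**Step 3: which reading is likelier?** Items i and k tolerate a limited amount of support, which favours the ceiling. The strict reading also leaves the figure of 2 L/min with nothing to do. Against that, items a and b are absence rules, and the opening words of item d fit that pattern. The ceiling is therefore the likelier intent, but this is inference.

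**Step 4: does another section settle it?**
- Inclusion criterion 11 requires pulmonary function testing but sets no minimum result. It leaves suitability to the physician's usual IL-2 criteria. It concerns screening and does not address oxygen before a dose.
- Table 4 in section 5.7 lists oxygen as a treatment for pembrolizumab infusion reactions, which is a different matter.
- Item b of the same checklist holds IL-2 for ongoing Grade 2 or worse events attributed to pembrolizumab. It does not cover oxygen need from IL-2 itself.

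None of these gives an oxygen limit for IL-2 dosing.

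**Step 5: how often is the line used?** Section 5.2.2 (Timing of Dose Administration) plans 8 IL-2 admissions, and Table 2 plans 5 doses in each: 8 × 5 = 40 planned doses per patient. This counts how often the item is consulted. It is not an estimate of wrong decisions, because the documents do not say how often patients need oxygen before a dose.

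**Step 6: link to the statistics.** The Simon design in section 8.4 (15 patients, then 9, for 24 in total) and the DLT boundary in section 8.5 (acceptable rate 0.15) contain no oxygen criterion. Neither changes with the wording of item d.

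**The case against.** The strongest reply is that nobody at the bedside would use the literal reading. It would require staff to look at a patient on, say, 4 L/min and conclude that the patient does not require 2 L/min or less and may therefore be dosed. The list defers to the treating physician, section 2.2 allows doses to be omitted for safety, and the synopsis places the trial in an experienced IL-2 center. Item b also holds some patients with lung toxicity whatever item d says. This reply largely stands. A reader might infer from the literal text that patients with higher oxygen need would actually be given IL-2. The documents do not support that: both plausible readings hold them, and physician judgment takes precedence over the list.

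A second reply is that the direction of the correction is uncertain. If a strict rule was meant, writing in a ceiling would loosen a safety criterion. This also stands, and it is why the sponsor must confirm the intent.

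Neither reply rescues the wording. The list gives numerical limits for creatinine, blood pressure, dopamine, urine output and boluses in order to inform the physician's judgment. A line that gets its limit backwards cannot do that. Nor does deferring to judgment tell the physician what the protocol intends for a patient on 1 or 2 L/min.

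Item h, on a heart rate continuously at 120, could likewise be read as exactly 120. That reading is pedantic, since a threshold is plainly meant, and item h is not part of this point.

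**Conclusion.** Item d is wrong as written and should be corrected. This follows from the text alone and rests on one assumption: that item d, like items i, j and k, states a condition for going ahead.

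The practical consequence is modest. The real uncertainty is confined mainly to the band above 0 and up to 2 L/min, where the ceiling and strict readings give opposite answers. Its size cannot be given from the documents. That the ceiling was intended is a reasonable inference from items i and k, not an established fact.

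A reader might also infer an effect on the efficacy result, since item d applies before the first IL-2 dose and that dose determines entry to the combination treatment population (section 8.3, Figure 7). The documents contain nothing to show or size such an effect, and none is claimed. ORR, the Simon design and the DLT boundary stand as they are.

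**What to change.** The sponsor should confirm the intended rule and replace item d with one of these:

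- Ceiling (the likely intent): *Requires no supplemental oxygen, or no more than 2 L/min, to keep oxygen saturation at 90% or above.*
- Strict rule, if that was meant: *Requires no supplemental oxygen to keep oxygen saturation at 90% or above.*

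Under the ceiling wording the three bands (0, above 0 to 2, above 2 L/min) become clear, clear, hold. Under the strict wording they become clear, hold, hold. Either way, need above 2 L/min is held.

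The cost is one line in the checklist, with no change to sample size, boundaries or schedule. If the list is being edited anyway, item h could be tidied to say at or above 120. That is optional.
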